**Statistical Methods:**

60 medical students will be consented to allow for dropout. Based on a repeated – measures design with one between-factor design (supine vs upright) and one within factor (repetitions), four groups with 10 subjects each with each subject measured 10 times, achieves 87% power to measure a difference in time to visualize the carina using a Geisser -Greenhouse Corrected F-test at a 5% significance level assuming an effect size of 0.7. Groups A ,B,C,D will be compared. The two outcome measures global rating scale (GRS) and examiner check list (ECL) scores will be analyzed using a two-way, mixed design ANOVA. Categorical data such as success failure will be analyzed by Fisher exact test. Time to intubation will be analyzed using the MannWhitney U test.

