**Phase one :**

Sixty medical students, novices in fiberoptic intubation use will be recruited and randomly assigned into one of two groups:

**Group A** (supine-supine) will first practice fiberoptic intubation with the iLarynx oriented in the supine position. Learning curves, global rating scale and checklist will then be obtained by a blinded examiner with the medical student using a real fiberoptic on a mannequin oriented in the supine, then upright position. At the end of one week, the same medical student will then perform the intubation with the mannequin in both positions.

**Group B** (upright-upright) will first practice fiberoptic intubation with the iLarynx oriented in the upright position. Learning curves, global assessment score and checklist will then be obtained by a blinded examiner with the medical student using a real fiberoptic on a mannequin oriented in the upright then supine position. At the end of one week, the same medical student will then perform the intubation with the mannequin in both positions.

**Group C** (supine –upright) will first practice fiberoptic intubation with the iLarynx oriented in the supine position. Learning curves, global assessment score and checklist will then be obtained by a blinded examiner with the medical student using a real fiberoptic on a mannequin oriented in the upright then supine position. At the end of one week, The same medical student will then perform the intubation with the mannequin in both positions.

**Group D** ( upright – supine) will first practice fiberoptic intubation with the iLarynx oriented in the upright position. Learning curves, global assessment score and checklist will then be obtained by a blinded examiner with the medical student using a real fiberoptic on a mannequin oriented in the supine, then upright position. At the

end of one week, the same medical student will then perform the intubation with the mannequin in both positions.

	teachin g		testing	testing		week	testing	testing
A	supine		supine	upright	i/droid	upright	supine	
B	upright		upright	supine	i/droid	supine	upright	
C	supine		upright	supine	i/droid	upright	supine	
D	upright		supine	upright	i/droid	upright	supine	

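### The plan leaves room to lose up to 20 of 60 students, but its ANOVAs by default exclude students with incomplete repeats; a mixed model on all observed attempts would be a cheap improvement

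*Combined protocol and SAP*

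**What the plan says.** **Numbers.** Under Phase one, "Sixty medical students, novices in fiberoptic intubation use will be recruited". Statistical Methods explains the figure: "60 medical students will be consented to allow for dropout". The power statement rests on "four groups with 10 subjects each with each subject measured 10 times", that is 40 students. The stated power is 87%, for time to carina; the test is a Geisser-Greenhouse F-test at the 5% level, and the effect size is taken as 0.7. No dropout rate is stated.

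**Analyses.** Repetitions are the only within-student factor named. GRS and ECL scores "will be analyzed using a two-way, mixed design ANOVA", and the within-student factor of that ANOVA is not named. Success or failure goes to Fisher's exact test and time to intubation to the Mann-Whitney U test.

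**Timing.** Each student is tested in both mannequin positions and then returns: "At the end of one week, the same medical student will then perform the intubation with the mannequin in both positions". Phase two also places its retest at one week. Retention is the third research question.

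**Missing data.** The document does not define an analysis set or say how missing attempts or missed retests are handled. It does not say that incomplete students will be excluded.

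**The concern.** Over-recruitment is the plan's only provision for loss. It protects the number analysed, but not the comparability of the randomised groups among those who remain.

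In their standard form, the two ANOVAs work on one complete row per student. Unless another rule is stated, a student who stops partway through the repetitions is dropped from the analysis of those repetitions. A student who misses the retest is dropped from any model that spans both sessions, and adds nothing to a model of the retest alone. Yet that student's first-session learning curves, GRS and checklist in both positions already exist, and they carry information about how the student would have done at one week.

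The retention comparison is therefore the most exposed. If return depends on first-session performance, a completer-only contrast can be biased, and the scores that could correct it go unused.

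**Working it through.** **1. The dropout allowance.** Inputs from Statistical Methods: 60 consented; 4 × 10 = 40 in the power statement. Allowance = (60 − 40)/60 = 33.3%. The reverse calculation, 40/(1 − 1/3) = 60, agrees, but only because the rate was derived from the same two numbers.

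**2. The stated 87% power.** This can be neither confirmed nor refuted, because the within-student correlation ρ and the meaning of the effect size of 0.7 are not given. For the between-group F-test with N students and m repeats, the noncentrality is λ = N·f²·m / [1 + (m − 1)ρ]. With N = 40, four groups and α = 0.05:

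| Reading of 0.7 | Setting | Power |
|---|---|---|
| f = 0.7 | single measure (m = 1) | 95.4% |
| f = 0.7 | m = 10, ρ from 0.9 down to 0 | 97% to 100% |
| f = 0.35 (0.7 read as a standardised difference) | m = 10, ρ about 0.27 | 87% |

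The present point does not depend on which reading is right. Losing 20 of 60 evenly leaves the planned 40, so there is no shortfall against planned power.

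**3. How quickly complete rows are lost.** Assume each of 10 attempts is independently missing with probability p. The share of students with all 10 is (1 − p)^10:

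- p = 1%: 0.99^10 = 0.90
- p = 2%: 0.98^10 = 0.82
- p = 5%: 0.95^10 = 0.60

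**4. Loss unrelated to performance.** There is no bias. Where 40 rather than 60 students are analysed, the standard error of a group contrast rises by √(60/40) = 1.22. For 30 against 30 in SD units it goes from √(2/30) = 0.26 to √(2/20) = 0.32. For first-session contrasts this applies only if the analysis is restricted to students complete across both sessions, or if the loss occurs within the first session.

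**5. Loss related to performance (simulation).** Assumptions, none of them from the documents: 30 against 30 by teaching orientation, true difference 0.50 SD at both visits, correlation 0.6 between visits, 20 of 60 lost, 4,000 replicates. The chance of loss is weighted by exp(k × first-session score in SD), where a higher score means slower. The last column uses every student's first-session score together with the observed retests.

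| k (relative weight of loss per SD) | First session, completers only | Retest, completers only | Retest, using first-session scores |
|---|---|---|---|
| 0 (1.0) | 0.50 | 0.50 | 0.50 |
| 0.5 (e^0.5 = 1.6) | 0.45 | 0.47 | 0.50 |
| 1 (e^1 = 2.7) | 0.39 | 0.43 | 0.50 |
| 2 (e^2 = 7.4) | 0.30 | 0.38 | 0.50 |

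In the limit where exactly the slowest 20 are lost, the completer figures are 0.25 and 0.35. The first-session column is subject to the same condition as step 4. The recovery to 0.50 in the last column follows from the set-up, because loss was made to depend on an observed score.

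**The case against.** The strongest reply is that the plan nowhere says it will discard anything. Several stronger readings are tempting, and the documents do not support them.

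- **That the plan expects a third of students to drop out.** It makes an allowance. The third is derived from 60 and 40, and no expected rate is stated.
- **That exclusion is a rule of the plan.** It is the usual behaviour of the named methods when nothing else is specified.
- **That a missed retest removes a student's Phase one data.** Only repetitions are named as a within-student factor. Unless session enters the same ANOVA, such a student stays in the first-session comparison.
- **That all group contrasts rest on completers.** Fisher's exact and Mann-Whitney tests do not need complete repeats.
- **That the trial becomes underpowered.** With even losses, the planned 40 remain.
- **That substantial bias is established.** Risks/Benefits says only that being evaluated may make students anxious, which is a general risk statement and not a prediction of dropout. Participants are students or interns on rotation, so scheduling is at least as plausible a reason for missing a one-week retest. The table in step 5 starts at no bias, and bias towards no difference follows only from the assumed mechanism.

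All of these limits stand. What remains is that neither an analysis set nor a missing-data method is given, and that the default of the named ANOVAs is less efficient, and less robust to performance-related loss, than a readily available alternative.

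**Conclusion.** The point holds as a cheap improvement to the analyses of time to carina, GRS and ECL; it does not show the trial to be invalid. By default those ANOVAs would exclude students with an incomplete set of repetitions and, in any model spanning sessions, students who miss the retest. The retention comparison would rest on completers without drawing on the first-session scores of those lost.

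If loss is unrelated to performance, the cost is precision only, up to 22% on the standard error where 40 rather than 60 are analysed. If slower students leave more often, the completer-only retest difference falls from 0.50 SD to between about 0.47 SD (weak selection) and 0.38 SD (strong selection). These figures rest on the simulation assumptions in step 5 and, for the full recovery, on missing at random given observed scores. Neither the amount of loss nor its mechanism can be known from the documents.

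**What to change.** Replace the ANOVAs for time to carina, GRS and ECL in Statistical Methods with a likelihood-based linear mixed model, fitted to all observed attempts of all randomised students in their assigned group. Specify:

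- **Fixed effects:** group, mannequin position, repetition and visit, with group-by-repetition, group-by-position and group-by-visit interactions. These carry the research questions on learning, transfer between positions and retention. If the Phase two practice allocation is analysed in the same model, it needs its own term at the retest.
- **Covariance:** a within-student structure that does not force equal correlation across attempts. A lone random student effect would impose the assumption that the planned Geisser-Greenhouse correction relaxes. A fully unstructured matrix over 10 attempts has 10 × 11/2 = 55 parameters, which is heavy for 40 to 60 students, so a structured choice, such as random effects with autoregressive residuals, should be named in advance.
- **Inference:** a small-sample degrees-of-freedom correction such as Kenward-Roger.
- **Reporting:** numbers lost by group, with the Phase one scores of those lost and those retained.

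Fisher's exact and Mann-Whitney analyses need no change on this account. The cost is one rewritten paragraph and somewhat more modelling work, with no new students or data. The model relies on missing at random given observed scores, which should be stated; the report of losses by group lets readers judge how plausible that is.

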**Research Aims:**

1. **Research Questions(s)** (1) Does spatial orientation of a novice in relation to a mannequin (supine vs upright) impact on the development of fiberoptic intubation skills (2) Is it necessary to teach both orientations or is the supine view transferable to the upright position. (3) Which method demonstrates longer skill retention.
  
2. **Hypotheses** (1) Both orientations must be practiced. (2) The upright skill is harder to learn but is retained for longer.

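### Test orientation is a named factor in no analysis, and no stated contrast isolates supine-to-upright transfer or orientation-specific practice

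*Combined protocol and SAP*

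**What the plan says.** In the combined protocol and SAP, Phase one says that students "will be recruited and randomly assigned into one of two groups" but then describes four. A and C practise supine; B and D practise upright. A and D are tested supine first; B and C are tested upright first. Every student is tested in both positions.

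The Research Aims ask "Is it necessary to teach both orientations or is the supine view transferable to the upright position" (question 2) and state as hypothesis 1 "Both orientations must be practiced".

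The Statistical Methods section describes the design as "one between-factor design (supine vs upright) and one within factor (repetitions), four groups with 10 subjects each" and then says "Groups A ,B,C,D will be compared". The global rating scale and checklist "scores will be analyzed using a two-way, mixed design ANOVA", without naming the two factors. "Time to intubation will be analyzed using the MannWhitney U test", without naming the two samples. Success or failure goes to a Fisher exact test. No test position or occasion is given for any of these comparisons.

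**The concern.** Question 2 concerns the practice difference at the upright test. Hypothesis 1 concerns whether the effect of practice depends on the position tested, which is a practice by test-orientation interaction. The plan ties no analysis to either.

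The between factor most naturally means practice orientation, since each student is tested in both positions and test position is therefore a within-student factor. The only within factor named is repetitions. The one comparison stated in words has four levels and bundles practice with the order of testing. A significant result could be read as an effect of practice orientation when it reflects learning between blocks. A real orientation-specific effect could also be missed. Learning between blocks is plausible: the students are novices and the study collects learning curves.

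**Working it through.** **1. The plan's own figure.** The inputs in Statistical Methods are 4 groups of 10, 10 measurements each, 5% level, effect size 0.7 and stated power 87%. For the between-group F-test the noncentrality is N·f²·10/(1+9ρ), where ρ is the within-student correlation.
- Effect size read as Cohen's f: 95.4% at ρ = 1 and higher below that, so never 87%.
- Effect size read as d (f = 0.35): 39% at ρ = 1, reaching 87% at ρ of about 0.27 (four groups) or 0.43 (two groups of 20).
- F-test on repetitions, f = 0.7, no Geisser-Greenhouse reduction: 88.6%.

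The correlation, the sphericity correction and the effect-size definition are not given, so 87% is neither confirmed nor refuted. The point does not depend on it.

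**2. Session-one layout (Phase one).**

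| Group | Practice | Supine test | Upright test |
|---|---|---|---|
| A | supine | block 1 | block 2 |
| B | upright | block 2 | block 1 |
| C | supine | block 2 | block 1 |
| D | upright | block 1 | block 2 |

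At either position, A–D and B–C differ in practice only, A–C and B–D in order only, and A–B and C–D in both.

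**3. Four groups compared at one position.** Assume one block mean per student, SD 1, 10 per group, no practice effect and a second-block gain of *o*. Two groups have mean 0 and two have mean *o*, so each lies *o*/2 from the grand mean. The noncentrality is 40·(*o*/2)² = 10*o*², with 3 and 36 df.

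| *o* (SD) | Noncentrality | F-test rejects |
|---|---|---|
| 0.25 | 0.625 | 8.5% |
| 0.5 | 2.5 | 21% |
| 0.7 | 4.9 | 39% |
| 1.0 | 10 | 71% |

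Order can also distort a real effect. Let upright practice help by 0.5 SD at the upright test, with a second-block gain of 0.5 SD. Then B minus A is 0.5 − 0.5 = 0, and D minus C is (0.5 + 0.5) − 0 = 1.0 SD.

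**4. Four groups compared at the first-tested block.** Order is now equal, but A and D are tested supine and B and C upright. If the upright test is harder by *h* SD and practice does nothing, the noncentrality is again 10*h*², so the rejection rates are those above with *h* in place of *o*. Hypothesis 2 itself expects the upright skill to be harder to learn.

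**5. Four groups compared on the average of both positions.** Order cancels, because each group has one first and one second block. A benefit *b* confined to the practised orientation, and equal in both, gives every group a mean of *b*/2. The F-test then has 5% power whatever *b* is.

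**6. The pooled contrast.** For A+C against B+D at the supine test, order contributes (0+*o*)/2 to one side and (*o*+0)/2 to the other, a difference of 0. In simulation this contrast rejected in 4%, 4% and 3% of null trials at *o* = 0.5, 0.7 and 1.0 SD without an order term, and in about 5% with one.

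Its order-adjusted power for a practice effect *b* at the upright test has noncentrality 40·*b*²/4 = 10*b*² (1 and 37 df): 34%, 58% and 87% at 0.5, 0.7 and 1.0 SD. First-test B against C has 20·*b*²/4 = 1.25 at 0.5 SD (1 and 18 df): about 19%.

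**7. One-week retest.** The Phase one table, as extracted, has A, C and D upright first and B supine first; Phase two says the order is random. Under the table, at the upright test A, C and D are in block 1 and B is in block 2. Order then adds *o*/2 to B+D and nothing to A+C, so pooling no longer removes it. For upright minus supine, order adds −*o* for A, C and D and +*o* for B, so A+C averages −*o* and B+D averages 0.

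**The case against.** The strongest reply is that session one is a balanced 2 × 2, so practice and order are orthogonal. The named between factor, if it means practice, is then the valid split A+C against B+D. This stands for the design. A reader might infer that practice and order are irretrievably confounded, and the documents do not support that.

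A reader might also infer that the plan commits to a four-group comparison at one position, so that 21% to 71% is the trial's false-positive rate. It does not: no position is stated, and the group labels fit the first-tested block at least as well. The order effect is assumed, and at 0.25 SD the rate is only 8.5%. Nor is rejection strictly an error for an omnibus test, since the sequences would truly differ; the error comes when the result is attributed to practice.

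Nor is order wholly absent, because the four group labels encode it at session one. The Mann-Whitney test can be read as A+C against B+D, and no set of pairwise tests is planned.

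The gap remains after all this. Test orientation is not named, the ANOVA factors are not named, the pooled contrast is not stated, and the only comparison stated in words uses four groups. The unnamed factors might have been meant to include test position, but nothing says so.

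**Conclusion.** The concern holds as a fault in the stated analysis that should be fixed; it is not a flaw in the session-one design. No named term or contrast answers question 2 or hypothesis 1, and each of the three readings of the four-group comparison in the working fails to isolate practice. That conclusion is structural and needs no numerical assumption. The 8.5% to 71% range is an illustration only: it applies to the one-position reading and rests on an assumed SD of 1, 10 per group, no practice effect and second-block gains of 0.25 to 1.0 SD. The validity of A+C against B+D without adjustment rests on roughly equal group sizes and applies to session one. At one week it depends on which test order is used.

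**What to change.** - For time to visualize the carina, the global rating scale and the checklist, replace the four-group sentence with a repeated-measures mixed model. Terms: practice orientation, test orientation, period (first or second block), repetition, practice × test orientation and practice × repetition. Code order as period, or equivalently as sequence × test orientation. A bare sequence main effect drops out of the upright-minus-supine difference and adjusts nothing there.
- Name the period-adjusted practice difference at the upright test (A+C against B+D) as the test of question 2. Name the practice × test-orientation interaction as the test of hypothesis 1.
- Keep Mann-Whitney for time to intubation and Fisher for success, but define both as A+C against B+D within each test position at session one, with one value per student per position.
- At one week, include period and the Phase two practice assignment, and reconcile the Phase one table order with the random order in Phase two.

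The cost is SAP wording and one reconciliation, with no new students or data. The model assumes no differential carry-over between blocks. First-test B against C and A against D can be reported as a check, but a weak one (about 19% power at 0.5 SD). The 87% power statement does not describe the new contrasts and should be labelled so.

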**Phase two:**

Study candidates will randomly be assigned (20 per group) to practice for 15minutes/day their intubations skills with the iLarynx application downloaded to their smart phones or Ipads. The other group (20candidates) will be asked not to practice their intubation skills. At the end of one week both groups will be retested on a mannequin by the same blinded examiner to obtain a new learning curve, global assessment score and checklist. Both orientations of the mannequin will be tested and the order randomly assigned.

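### Success/failure is assigned Fisher's exact test, which needs one independent result per student, in a repeated-measures design that names no per-student result

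*Combined protocol and SAP*

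**What the plan says.** Statistical Methods gives success/failure one sentence: "Categorical data such as success failure will be analyzed by Fisher exact test". Success is not defined. The section does not say whether the unit is the attempt or the student, which position or session is meant, or how several results from one student would be combined.

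The same section describes a repeated-measures design, "four groups with 10 subjects each with each subject measured 10 times", with repetitions as the within-student factor. Time to the carina is powered with a corrected repeated-measures F-test, and the rating scale and checklist get a mixed ANOVA. Only success/failure and time to intubation are given tests for independent observations; this point concerns the former.

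Phase one tests each student in both positions in the first session (for Group A, "using a real fiberoptic on a mannequin oriented in the supine, then upright position"). One week later "the same medical student will then perform the intubation with the mannequin in both positions". Phase two retests both orientations "to obtain a new learning curve, global assessment score and checklist", with 20 students per arm.

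**The concern.** Fisher's exact test assumes that every entry in the table is a separate, independent observation. A student who handles the scope well tends to succeed repeatedly, so attempts by one student are correlated. Pooling them counts the same student several times and can make chance differences look significant. Taking one attempt per student avoids that but leaves most of the data unused.

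Two of the three research questions, transfer between positions and retention, draw on comparisons within the same student. There the two columns of a Fisher table hold the same people, and the test cannot use that pairing.

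Because the unit is left open, it could also be chosen after the results are seen.

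**Working it through.** **The plan's own figure.** No figure is given for success/failure. The stated 87% power is for time to the carina and cannot be reproduced uniquely, because the within-student correlation, the sphericity correction (ε) and the scale of the 0.7 effect size are missing. One nearby value is 88.6%, from a within-factor test with λ = 40 × 0.7² = 19.6 and ε = 1. Nothing below depends on it.

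**Inputs from the documents.** 10 students per group (Statistical Methods); 20 per arm (Phase two); 2 positions × 2 sessions = 4 position tests per student (Phase one); 10 measurements per student (Statistical Methods, in the power statement).

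**Assumptions.** True success 75% in both groups for false positives, and 85% vs 55% for power; within-student correlation ρ from 0.05 to 0.4; a constant success rate over attempts (beta-binomial counts); two-sided 5% level; two groups compared.

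**1. Pooled results.** Clustering multiplies the variance of a group's success proportion by 1 + (m − 1)ρ, where m is the number of results per student. The false-positive rates come from exact enumeration of Fisher's test on the pooled counts.

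| m | 1 + (m − 1)ρ at ρ = 0.05 and 0.4 | False positives, 10 vs 10 | False positives, 20 vs 20 |
|---|---|---|---|
| 2 | 1.05 and 1.4 | 2.7–5.8% | 3.3–6.5% |
| 4 | 1.15 and 2.2 | 4.1–14.5% | 4.7–15.3% |
| 10 | 1.45 and 4.6 | 7.8–33.2% | 8.5–33.8% |

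Simulation put the upper end for m = 4 at 16%. In round figures the ranges are 3–6%, 4–16% and 8–34%. With two results the rate stays near 5% because Fisher's test is conservative to begin with: with independent attempts it rejects about 3–4% of the time at m = 10.

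A rough hand check for m = 10 and ρ = 0.4: 1.96/√4.6 = 0.914, and 2Φ(−0.914) ≈ 36%. This is slightly above the exact 33–34%, as Fisher's conservatism would lead one to expect.

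**2. One attempt per student.** The test is valid, with type I error of about 1–3%. Exact power for 85% vs 55% is 14.1% with 10 vs 10 and 44.3% with 20 vs 20.

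**3. All attempts, student as the unit.** With 10 attempts per student and ρ from 0.4 down to 0.1, a permutation test on each student's success count rejects 3–4% of the time under no difference. Its power for 85% vs 55% is 54–88% with 10 vs 10 and 86–99.8% with 20 vs 20.

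**4. Upright vs supine within students.** Take 40 students, one result per position, assumed success of 85% and 60%, and a latent correlation of 0.5. Fisher's test has 66% power and exact McNemar has 77%.

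**The case against.** The strongest reply is that the sentence is incomplete rather than wrong. Fisher's test is sound for a between-group comparison if each student contributes one binary result built from all attempts. For illustration, scoring a student as successful with at least 8 of 10 successes, under the same assumptions and ρ from 0.1 to 0.4, gives type I error of about 1–2.5%. Power falls from 60% to 27% with 10 vs 10, and from 95% to 67% with 20 vs 20. That is less than the permutation test but well above a single attempt. This stands: pooling and picking one attempt are not the only readings. But the plan names no such summary, and none would make Fisher's test suitable for paired comparisons.

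It also stands that "each subject measured 10 times" belongs to the power statement for time to the carina. A reader might infer 100 scored successes or failures per group (10 × 10) and a false-positive rate several times 5%. The documents do not support that as fact: they do not say that success is scored on every repetition, or whether the 10 are per position, per session or in total. With two results per student the rate is close to nominal.

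The calculations compare two groups at a constant success rate, whereas the plan compares four groups and expects learning. They show the size of the problem rather than predict it. A logistic mixed model was not tested at this sample size.

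**Conclusion.** The concern holds in conditional form. The plan assigns a test for independent observations to an outcome from a repeated-measures design and names no single result per student. Nothing else in the document repairs this.

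- **Pooling:** the false-positive rate runs from about nominal to about 34%, depending on the number of scored results and the correlation. Both are assumed here.
- **One attempt per student:** valid but weak, especially at 10 per group.
- **Position and session contrasts:** Fisher's test ignores the pairing. With one result per condition it costs power, about 11 points in the example (77 − 66).

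A reader might go further and conclude that the trial's sample size or main analysis is undermined. It is not. Success/failure is neither the powered outcome nor one of the two scores that receive a mixed ANOVA, so the consequence is confined to the success/failure analysis. The change should be made, but it does not call the design into question.

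**What to change.** In Statistical Methods, define success, state which attempts, positions and sessions are scored, and make the student the unit of analysis. Then:

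- **Between groups:** compare each student's number of successful attempts with a permutation or rank test.
- **Within students (position, session):** use a signed-rank or sign-flip permutation test on each student's difference in success proportion, or exact McNemar if there is one result per condition.
- **Supporting analysis:** a logistic model with a random student effect. It should not be the main analysis, because it may be unstable with about 10 students per group.
- **Fisher's exact test:** keep it only for outcomes recorded once per student, including any prespecified binary summary.

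The cost is a sentence or two of text and slightly more analysis work. No new data and no change in sample size are needed.

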***EXAMINER CHECKLIST***

		CORRECTLY	INCORRECTLY
1	Hold control section correctly in one hand with thumb positioned for flex/ext control, and index finger for suction		
2	Focuses scope using appropriate external object		
3	Controls tip of scope with other hand		
4	Introduces bronchoscope into mouth, centered		
5	Maneuvers bronchoscope through oropharynx and visualizes cords		
6	Passes cords		
7	Continues insertion of bronchoscope to level of carina		
8	Passes endotracheal tube atraumatically		
9	Reconfirms vision of carina after ET tube in situ		
10	Removes bronchoscope smoothly		
11	Checks for etCO 2		

Time Elapsed: \_\_\_\_\_

Overall Rating: \_\_\_\_\_

**Consent:** Attached

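### Time to intubation is assigned a two-sample Mann-Whitney U test, which cannot make the plan's four-group comparison or use its repeated attempts

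*Combined protocol and SAP*

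**What the plan says.** All of the analysis text is in one paragraph, Statistical Methods.

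- **Design for the power statement:** "one between-factor design (supine vs upright) and one within factor (repetitions"), with "four groups with 10 subjects each with each subject measured 10 times".
- **Powered outcome and test:** a "difference in time to visualize the carina using a Geisser -Greenhouse Corrected F-test", at 5% significance, effect size 0.7, power 87%.
- **Comparison:** "Groups A ,B,C,D will be compared".
- **Global rating scale and checklist score:** a mixed-design ANOVA.
- **Success or failure:** Fisher's exact test.
- **Time to intubation:** "Time to intubation will be analyzed using the MannWhitney U test". Nothing further is said about this outcome.

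Under Phase one, every student is tested in both mannequin orientations and again after a week. Under Phase two, two groups of 20 (practice, no practice) are retested in both orientations, and a new learning curve is obtained.

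The Examiner Checklist has a single Time Elapsed blank with no start or stop event. The carina appears on it twice: "Continues insertion of bronchoscope to level of carina" (item 7, before the tube) and "Reconfirms vision of carina after ET tube in situ" (item 9, after it).

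**The concern.** A Mann-Whitney U test takes two independent samples and one observation per independent unit. The paragraph that assigns it describes four groups and ten measurements per student. The test has no four-group form, no term for attempt, and no way to allow for attempts that are correlated within a student.

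The analyst must therefore make choices that the plan does not settle: which two groups, which attempt or summary, which orientation, which session, and what to do about multiplicity. Some of these choices are sound and some badly inflate the false-positive rate. The first research question asks whether orientation has an "impact on the development of fiberoptic intubation skills", so how time changes over attempts is of direct interest, and a test that takes one value per student uses it only if that value is chosen to capture it.

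A related point concerns data capture. The plan has two time outcomes, but one undefined blank cannot hold both for the same attempt.

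**Working it through.** **1. Inputs.** From Statistical Methods: 4 groups, 10 students per group, 10 measurements per student, alpha 0.05, effect size 0.7, power 87%. From Phase two: 20 versus 20. The documents give no within-student correlation (rho), no sphericity value (epsilon) and no definition of the effect size. The values of rho and epsilon below are assumptions, shown as ranges, and so is a level of 0.05 for each Mann-Whitney test.

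**2. The plan's own figure.** The 87% can be neither confirmed nor refuted, because the tested term, effect-size definition, rho and epsilon are not stated. Noncentral F power under several readings:

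| Reading | Noncentrality | df | Power |
|---|---|---|---|
| Four groups, f = 0.7, one value each | 40 × 0.7² = 19.6 | 3, 36 | 95.4% |
| Two groups of 20, 0.7 read as d (f = 0.35), one value each | 40 × 0.35² = 4.9 | 1, 38 | 57.8% |
| Attempt effect, f = 0.7, epsilon 1 / 0.75 / 0.5 | 19.6 × epsilon | 9 and 324, × epsilon | 88.6% / 80.4% / 67.0% |
| Four-group group × attempt term, f = 0.7, epsilon 1 | 19.6 | 27, 324 | 66.0% |

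None of these concerns a rank test on time to intubation. The 87% is not disputed here; it simply does not cover that analysis.

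**3. If all group pairs were tested.** Four groups give 4 × 3 / 2 = 6 pairs. Six independent tests at 0.05 would give 1 − 0.95⁶ = 26.5%. The pairs share groups and the rank test is discrete, so the true figure is lower. Simulation with 10 students per group, one value each and no true difference gives 18.2% (20,000 runs) and, in a separate run, 18.9% (10,000 runs). One Kruskal-Wallis test on the same kind of data gives 4.6%.

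**4. If attempts were pooled as independent.** With equal correlation rho among 10 attempts, the variance of a group mean is inflated by 1 + 9·rho. The approximate type I error is 2 × [1 − Φ(1.96 / √(1 + 9·rho))]. Simulation used 10,000 runs with normal data; the Mann-Whitney result is the same on the log scale.

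| rho | 1 + 9·rho | Formula | Simulated, 10 vs 10 | Simulated, 20 vs 20 |
|---|---|---|---|---|
| 0.1 | 1.9 | 15.5% | 15.3% | 15.1% |
| 0.3 | 3.7 | 30.8% | 30.1% | 29.8% |
| 0.5 | 5.5 | 40.3% | 40.2% | 40.1% |
| 0.7 | 7.3 | 46.8% | 47.0% | 47.1% |

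At rho = 0 the simulated rates are 4.7% and 4.8%, as they should be.

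**5. If one mean per student were used in one two-group contrast.** The test is then valid. Its power depends on choices the plan leaves open. Reading 0.7 as a shift of 0.7 SD of a single attempt (an assumption), with variance (1 + 9·rho) / 10 for a student's mean, simulated power at rho 0.3 / 0.5 / 0.7 is 62.8% / 47.0% / 36.8% for 10 versus 10 and 93.0% / 81.0% / 68.6% for 20 versus 20.

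**The case against.** The strongest reply is that two-group contrasts do exist. The between factor in Statistical Methods has two levels, supine and upright, and Phase two compares practice with no practice. With one value per student, Mann-Whitney is valid for either. This stands, and a reader who inferred that the test is wrong in itself would go too far. It does not rescue the sentence as written: the plan ties the test to neither contrast, names no summary value, and says that all four groups will be compared.

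Other stronger readings are also unsupported.

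- **That error rates of 18-19% or 15-47% are what the trial will have.** No section proposes unadjusted pairwise testing or pooled attempts. The figures show what the wording leaves open.
- **That Mann-Whitney must miss differences in learning rate.** This depends on the summary. In a simulation with group slopes of +s and −s that cross mid-series, and s tuned so that the corrected F-test has roughly 87% power, Mann-Whitney on student means detects about 5%. The same test on each student's fitted slope, 20 versus 20, detects at least 99.9%. The 5% reflects equal averages by construction, and the tuned 87% is not the plan's 87%.
- **That one time blank contradicts ten measurements.** A form could be completed for each attempt; the documents do not say.
- **That time to the carina will be lost.** Learning curves are listed separately from the checklist, and the documents do not say that the checklist is the only place where times are recorded.

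It is also fair that the power sentence pairs the F-test with time to the carina and not with time to intubation. These are two outcomes, and only the first sets the sample size.

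**Conclusion.** The point holds in this form: the only method stated for time to intubation does not fit the comparison and the repeated measurements stated in the same paragraph. This is more than missing detail, because a named test is set against a design that it cannot analyse, and better-fitting methods are readily available.

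Its size depends on how the test would be used: about 18-19% familywise error for six unadjusted pairs with 10 students per group, about 15-47% type I error for pooled attempts at rho 0.1-0.7, and no inflation for one named contrast with one value per student. These results rest on assumed correlations, equal correlation between attempts, and 0.05 per test.

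The form point holds only in part. A single Time Elapsed blank without an end point cannot supply both time outcomes for one attempt; whether times are also kept elsewhere is not stated.

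The 87% should be read only as a statement about time to visualize the carina under the corrected F-test.

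**What to change.** 1. **Phase one, time to intubation.** Use a repeated-measures ANOVA (Geisser-Greenhouse corrected) or a linear mixed model of log time with group (A, B, C, D), attempt and group × attempt, and student as the repeated unit. Handle mannequin orientation explicitly, either by separate analyses or as a second within-student factor. State how failed attempts, which have no intubation time, are treated.
   *Alternative:* Kruskal-Wallis on one pre-stated summary per student (a mean, or a slope if learning rate is the target), followed by Holm-adjusted pairwise tests.
2. **Mann-Whitney.** Keep it only for a named two-group contrast with one value per student and orientation, such as practice versus no practice in phase two, and say which value is taken from the new learning curve.
3. **Checklist.** Replace the single blank by two times, each with a defined start and end point: first view of the carina (item 7, the powered outcome) and intubation (for example, ending at item 9).
4. **Power.** Do not extend the 87% to time to intubation.

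The cost is a few sentences in Statistical Methods and one extra line on the form, settled before testing starts. No change to the groups or to enrolment is needed for these edits.
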